Biopsy forceps commonly used for TBLB via the flexible bronchoscope are generally of the order of 3 mm or smaller in any given dimension. Because of this restriction in size, tissue samples obtained via the transbronchial approach are generally 2–3 mm in any dimension. Despite the small size, TBLB provides information regarding pathology that is located beyond the cartilaginous airways that may include elements of the small airways of the distal bronchial tree, the alveolar space, the vasculature, and lymphatic structures immediately surrounding the alveoli (6). Pulmonary diseases that require examination of larger pieces of lung tissue to assess heterogeneity or homogeneity of different regions of the involved lung, such as many of the idiopathic interstitial lung diseases, are generally not amenable to diagnosis by TBLB and consideration of video-assisted thoracoscopic lung biopsy, which has been shown to have a greater diagnostic yield (7,8), should be pursued. With these limitations in mind, TBLB is useful for the diagnosis of a variety of infectious, interstitial, and malignant pulmonary diseases, including pulmonary infiltrates in the immunocompromised host (9,10), sarcoidosis (11,12), eosinophilic lung disease (13,14), drug-induced pneumonitis (15), pulmonary alveolar proteinosis (16), lung cancer (17), pulmonary lymphangitic carcinomatosis (18,19), and acute allograft rejection in lung transplant recipients (20,21). Absolute contraindications for TBLB include inability to obtain informed consent, severe or refractory hypoxemia, uncontrolled bronchospasm, and unstable cardiovascular condition, including active ischemia and uncontrolled arrhythmia. Relative contraindications include uncorrected coagulopathy, platelet count of less than 50 K/ μ L, severe pulmonary hypertension, uncooperative patient, inability to control cough, and lack of resuscitation facilities (22,23).

Technique

A thorough airway examination usually precedes the TBLB because bleeding after lung biopsy may preclude its performance. Adequate control of cough with topical application of lidocaine

and systemic administration of opiates is recommended for optimal biopsy procedure and to reduce the risk of pneumothorax (24).

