In the PROPHET trial, we intend to assess the degree of biopsy-related bleeding, measures taken to control bleeding, and potential effects of bleeding on completion of the intended procedure in 100 bronchoscopy procedures performed on single and double lung transplant recipients, randomized to prophylactic topical epinephrine versus placebo (normal saline). The study participant, physician performing the TBLB, and independent observer reviewing the procedure recording will all be blinded to the randomization. Further use of measures to control bleeding that occurs during the procedure as well as the decision to complete the procedure as planned or to abort it prematurely will be left to the discretion of the performer. In this way, we aim to elucidate a potential role of topical epinephrine in the prevention of TBLB-related airway bleeding in lung transplant recipients and assess whether the dose and volume of instillation used in our institution comprises an effective means to prevent hemorrhagic complications of TBLB.

HYPOTHESIS

We hypothesize that prophylactic instillation of topical epinephrine prior to performance of TBLB will decrease the frequency and extent of biopsy-related hemorrhage as well as result in fewer procedures being aborted earlier than intended due to bleeding complications as well as shorter overall procedure time due to the preventive effect on bleeding. Concomitantly, we hypothesize that the instillation of topical epinephrine will not be associated with a serious adverse event profile in comparison to placebo.

SPECIFIC AIMS

In this randomized-controlled double blind placebo controlled clinical trial post-lung transplant patients scheduled to receive bronchoscopy with TBLB as part of their routine standard of care will be randomized to receive a fixed dose and volume of topical endobronchial epinephrine versus matching volume of placebo which will be instilled into the target biopsy airway prior to performance of TBLB. Our study will specifically aim at providing the following information:

Aim 1: Demonstrate the feasibility of assessments of bleeding related to TBLB, including:

1. The degree of TBLB-related bleeding using a standardized grading scale used by the physician performing the procedure to quantify the degree of procedure-related bleeding.

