2. The degree of TBLB-related bleeding using a standardized grading scale used by two independent observers blinded to patient data and study drug assignment who will review a video recording of the procedure to quantify the degree of procedure-related bleeding.
3. The magnitude of inter-observer variability in grading TBLB-related hemorrhage based on review of video recording of the procedure.

Aim 2: Evaluate the hypothesis that prophylactic administration of topical epinephrine results in reductions in TBLB-related hemorrhage in lung transplant recipients, including:

1. The frequency of active measures taken to control pulmonary hemorrhage once it occurred.
2. The proportion of procedures completed as planned in terms of obtaining a predefined target number of biopsy specimens.
3. Comparison between single- and double-lung transplant recipients in terms of prevalence and degree of TBLB-related hemorrhage.
4. Identification of clinical factors associated with an increased or decreased risk of procedure-related hemorrhage.

Aim 3: Evaluate the hypothesis that prophylactic administration of topical epinephrine affects the overall efficiency of bronchoscopy with TBLB performance, including:

1. Overall duration of the bronchoscopic procedure.

2. The proportion of procedures completed as planned in terms of number of adequate biopsies obtained as assessed by the physician performing the bronchoscopy.
3. The proportion of procedures resulting in acquisition of adequate biopsy samples that allows proper pathologic evaluation of assignment of a pathologic diagnosis.

Aim 4: Explore the hypothesis that instillation of our prespecified dose and volume of topical epinephrine into the target biopsy airway is not associated with an adverse event profile that is significantly different from placebo, including:

1. The prevalence of clinically significant hemodynamic changes.
2. The prevalence of cardiac adverse events, including conduction abnormalities, arrhythmia, and myocardial ischemia.
3. The prevalence of other vascular adverse events, including stroke, mesenteric ischemia, and critical limb ischemia.
4. Identification of clinical factors associated with an increased or decreased risk of drug-related adverse events.

STUDY PROTOCOL

Overview

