Any potential PROPHET participants who meet initial screening criteria and are anticipated to undergo bronchoscopy with TBLB will undergo a thorough chart review conducted by a member of the research team. Demographics, past medical history and comorbid conditions, indication for lung transplant, indication for bronchoscopy with TBLB and possible concurrent procedure(s), prior complications related to bronchoscopy or TBLB, current and active medications, most recent pulmonary function tests, and most recent report of echocardiogram will be reviewed to ensure inclusion and exclusion criteria are met. Recent laboratory data including complete blood count, comprehensive metabolic panel, coagulation studies, and 12-lead electrocardiogram will be reviewed following our institutional standard protocol for bronchoscopy.

On the day of procedure, as per our institutional procedural protocol, participants will have intake vital signs obtained. Recent history and physical examinations dated within 30 days of procedure will be reviewed or obtained if not available. Participants will be monitored under telemetry starting with this intake period, during and approximately an hour after conclusion of procedure unless procedural complication merit additional closer monitoring.

Monitoring Subjects and Criteria for Withdrawal of Subjects from the Study

Before and after the procedure, on the procedure day, study participants will be monitored in the UMMC endoscopy peri-procedure suite (for outpatients) or in the admitting unit (for inpatients). An on-call pulmonary physician will be available to assist with any immediate issues. During the procedure, study participants will be monitored by the UMMC bronchoscopy suite nursing staff, the performing bronchoscopist, and any additional physicians participating in the procedure. We do not anticipate problems requiring withdrawal of patients from the PROPHET study once enrolled, other than by the patient's request. In the event a study subject elects to be withdrawn from the study and requests their data to be withdrawn as well, we will comply.

Study Drug and Placebo Preparation, Packaging, and Randomized Assignment

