3. Per local protocol, peri-procedurally and during the procedure, the patient's heart rate, electrocardiography rhythm strip, respiratory rate, and oxygen saturation will be monitored continuously. Blood pressure will be repeatedly measured every 3 minutes. Up to 6 liters of supplemental oxygen via nasal cannula will be given in order to maintain an oxygen saturation of >92%. A defibrillator as well as a resuscitation drugs and equipment are available at all times in the bronchoscopy suite.
4. Patient will undergo the procedure in the supine position on an adjustable bed. Premedication will be performed per local protocol, including inhalation of 5 mL of 4% lidocaine via a nebulizer. Gurgling of 2 to 4 mL of 2% liquid lidocaine (20-40 mg) for upper airway anesthesia may also be applied depending on the performing bronchoscopist's preference. Moderate sedation will be achieved with a combination of midazolam (maximal dose of 6 mg per procedure) and fentanyl (maximal dose of 300 mcg per procedure). Laryngeal and lower airway anesthesia during the procedure will be obtained with the use of 2 mL aliquots of 2% liquid lidocaine up to a cumulative liquid lidocaine dose of 400 mg. A bite block will be used for procedures performed through the transoral approach. For the transnasal approach, 2% viscous lidocaine will be applied with a cotton swab to the chosen nostril and nasal passage to allow easy advancement of the bronchoscope.
5. Bronchoscopy will be performed with an Olympus BF-1T160 or BF-1TH190 (Olympus, Tokyo, Japan) video bronchoscope under fluoroscopic guidance (OEC 9900 Elite Mobile C-arm, GE Healthcare, Chicago, Illinois, United States).
6. For the purpose of independent post-procedure analysis, the entire procedure from insertion of the bronchoscope into the airways until its final retraction will be video-recorded on DVD media and individually labeled without disclosing study arm assignment. DVDs will be stored with other individual patient study documents for later review. Access to the stored DVDs will be provided only to the PROPHET study research team.

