7. Prior to biopsy performance 2 mL of 1:10,000 diluted epinephrine followed by 8 mL of ambient room air or 2 mL of sterile saline solution followed by 8 mL of ambient room air as described in "Study Drug and Placebo Preparation" will be instilled into the target airway by the bronchoscopist. This process may be repeated once, should the performing bronchoscopist choose to perform additional biopsy passes through a different airway. If choose to do so, the same study drug will be instilled into both airways. Any additional biopsies performed, will be done without airway instillation of study drug.
8. Biopsies will be performed using brand bronchoscopic biopsy forceps as preferred by the procedure performer. For ACR, aim will be to obtain 5 to 8 adequate biopsies, preferably from

the lateral subsegment of either the right or left lower lobes to allow optimal visualization and minimize forshortening under fluoroscopy as well as to avoid as much as possible spillage of blood into uninolved lung segments in the event of biopsy-related hemorrhage as described above. For the evaluation of radiological findings, aim will be to obtain 4 to 8 adequate biopsy specimens from an involved segment in one of the lungs based on imaging. All bronchoscopies will be performed by an experienced bronchoscopist.

9. The following data will be recorded with regard to the performance of the procedure:
 - 9.1. Patient study-arm assignment – recorded in a separate database.
 - 9.2. Indication for bronchoscopy with TBLB.
 - 9.3. Target number of TBLB specimens and target lobe and segment.
 - 9.4. Name and dosages of all medications administered to the patient in the hospital during the day of the procedure, including medications frequently administered during bronchoscopy such as topical anesthetic agents, sedation and analgesia agents, and hemostatic agents. Study drug vs. placebo administration will be recorded as described previously under “*Randomization*” and “*Study Drug and Placebo Preparation and Packaging*”.
 - 9.5. Supplemental oxygen requirements which exceed patient’s baseline requirements during or following the procedure.
 - 9.6. Any hemodynamic, cardiac, or respiratory events as recorded by telemetry in the procedure suite and/or in the recovery suite following the procedure.
 - 9.7. Bronchoscope model, including outer diameter and inner diameter of working channel.

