Moderate	Any bleeding originating from the biopsy target airway requiring in addition to maneuvering the bronchoscope application of iced saline or topical epinephrine or placing the patient with the bleeding lung in the dependent position
Severe	Any bleeding originating from the biopsy target airway requiring, in addition to the above-mentioned maneuvers, early termination of the procedure or necessitating application of balloon tamponade, endotracheal intubation, application of a bronchial blocker, or use of other invasive measures to achieve hemostasis, such as bronchial artery embolization or surgical intervention

4. Number of forceps passes performed.
5. Number of adequate tissue samples obtained.

6. Early termination of the procedure due to bleeding complication, defined as non-achievement of the target number of tissue samples as designated by the performing bronchoscopist prior to the procedure related to hemorrhage.
7. Duration of the procedure from first bronchoscope insertion to last bronchoscope withdrawal.
8. Total volume of iced saline used during the procedure.
9. Total dose of unblended topical epinephrine used during the procedure.
10. Any use of hemostatic procedures including balloon tamponade, endobronchial blocker, bronchial artery embolization, emergency surgery.
11. Any use of devices or procedures with intention of securing the airway including oral airway, nasal airway, laryngeal mask, endotracheal intubation, emergency cricothyroidotomy, and emergency tracheostomy.
12. Unplanned admission to the hospital or escalation in level of care within 48 hours of the procedure.
13. Pathologic diagnosis achieved.

Safety Outcomes

The safety of topical epinephrine administration and potential instillation-related adverse events will be derived from clinical monitoring, vital signs, and ECG recordings during and immediately following the procedure as well as from any clinical, laboratory, or radiologic investigations performed during or following the procedure. Complications deemed related to topical epinephrine administration and comprise the study safety outcomes include:

1. All-cause mortality within 3 hours of instillation of the study drug.
2. Acute cardiovascular event, including cardiac arrest, new onset chest pain, acute myocardial ischemia, pulmonary edema, acute ischemic stroke, critical limb ischemia, acute mesenteric ischemia, occurring within 30 minutes of instillation of the study drug.

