Data are expressed as means with standard deviations, medians with interquartile range, percentages, and proportions as appropriate. Continuous outcome variables were visually examined for normality and outliers using histograms and scatter plots. The normal distribution was assessed with the Shapiro-Wilk test. Continuous variables were compared with the Student's t-test for normally distributed data with similar variance and the Mann-Whitney tests for non-normally distributed data. Proportions were compared using Chi-squared or Fisher's exact tests as appropriate. Statistical significance was set at $P<0.05$. All statistical analyses were performed based on original assigned groups and using Stata software, version 14 (Stata Corp LLC).

Potential Benefits

We hypothesize that prophylactic instillation of topical epinephrine prior to TBLB will reduce procedure-related hemorrhage, leading to lower rate of prematurely aborted procedure due to bleeding complications and higher yield of intended biopsies. The participants may, therefore, have direct benefit from participation if prophylactic topical epinephrine reduces the rate of procedure related hemorrhage in TBLB therefore avoiding early termination of procedure and more intended biopsies taken providing a higher diagnostic yield.

No financial reimbursements or incentive for participating in the PROPHET study will be provided.

Potential Risks and Discomforts

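### Procedure duration is compared without adjusting for time the study drug cannot affect, which costs precision but causes no bias

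*Combined protocol and SAP*

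**What the plan says.** Secondary Efficacy Outcomes, item 7, defines the outcome as "Duration of the procedure from first bronchoscope insertion to last bronchoscope withdrawal". This matches Specific Aims, Aim 3, item 1 ("Overall duration of the bronchoscopic procedure") and the Hypothesis section, which expects "shorter overall procedure time due to the preventive effect on bleeding".

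Under Procedure Performance, item 7, the study drug or saline "will be instilled into the target airway by the bronchoscopist" before biopsy, so it is given through a scope already in place. The Introduction (Technique) notes: "A thorough airway examination usually precedes the TBLB because bleeding after lung biopsy may preclude its performance". Procedure Performance, item 4, has laryngeal and lower airway lidocaine given during the procedure. Exclusion criterion 4.11 permits lavage and endobronchial biopsy in the same session, and other procedures that may bleed if they follow the transbronchial biopsy.

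For timing, Procedure Performance item 9.8 lists scope insertion and completion only. Item 6 states that "the entire procedure from insertion of the bronchoscope into the airways until its final retraction will be video-recorded on DVD media".

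For analysis, the Data Analysis section gives Student's t-test for "normally distributed data with similar variance and the Mann-Whitney tests for non-normally distributed data". It names no covariate or stratification factor.

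**The concern.** The hypothesised saving comes from less bleeding, so it can arise only after instillation. Minutes spent earlier on airway inspection and anaesthesia cannot be shortened by a drug not yet given, yet they count in full. Permitted concurrent procedures also vary from one session to another and are timed. An unadjusted comparison leaves all this variation in the error term.

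What is at stake is precision for a stated hypothesis. The Overview plans 100 procedures, and the Sample Size section says that numbers rest mainly on feasibility, so there is no designed margin to absorb avoidable variance. A real saving in minutes could be reported with an interval too wide to be informative.

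**Working it through.** **No plan figure to reproduce.** The documents give no mean, standard deviation, target difference or power for duration. What follows is illustration under stated assumptions.

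**Set-up.** Total duration = pre-instillation time + post-instillation time. Let the post-instillation SD be 1, the pre-instillation SD be *s*, and their correlation be *r*. The 100 procedures are treated as independent and split 50:50.

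- Var(total) = 1 + s² + 2rs
- corr(total, pre)² = (s + r)² / Var(total)
- SE after adjustment / SE before = √(1 − corr(total, pre)²)

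**Independent segments (r = 0).** Here corr² equals *f*, the pre-instillation share of the total variance.

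- f = 0.25: √0.75 = 0.866, so the SE falls 13%; equivalent sample-size factor 1/0.75 = 1.33.
- f = 0.50: √0.50 = 0.707, so the SE falls 29%; equivalent factor 1/0.50 = 2.

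**The same in power terms (r = 0, two-sided 5% assumed because the plan does not state sidedness).** Take the difference that has 80% power after full adjustment: √(2/50) × (1.960 + 0.842) = 0.560 post-instillation SDs. Without adjustment the SD is 1/√(1 − f).

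- f = 0.25: SD 1.155; Φ(2.802/1.155 − 1.960) = 67.9% power.
- f = 0.50: SD 1.414; Φ(2.802/1.414 − 1.960) = 50.8% power.

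**Correlated segments (s = 0.5).**

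| r | Var(total) | Pre-time share, s²/Var | corr² | SE factor | Fall in SE |
|---|---|---|---|---|---|
| +0.25 | 1.50 | 17% | 0.375 | 0.791 | 21% |
| 0 | 1.25 | 20% | 0.200 | 0.894 | 11% |
| −0.25 | 1.00 | 25% | 0.0625 | 0.968 | 3% |
| −0.50 | 0.75 | 33% | 0 | 1.000 | 0% |

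The share of variance alone does not fix the gain. A share of 25% gives 13% under independence but 3% at r = −0.25.

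**Validity of the planned test.** In simulation with coin-toss allocation and no true effect (3,000 runs per setting, shares from 0 to 75%), the unadjusted t-test and Mann-Whitney test rejected in 4.5% to 5.8% of runs, close to the nominal 5%.

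**Validity of the covariate.** Insertion-to-instillation time is observed after allocation but before any drug is given, and the bronchoscopist is blinded. Arm therefore cannot influence it, and adjusting for it does not remove part of the effect.

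**The case against.** The strongest reply is that the plan is coherent as it stands. The aim is overall duration, item 7 measures overall duration, and random blinded allocation balances pre-instillation time in expectation. On this view, adjustment is an optional refinement for one of 13 secondary outcomes in a pilot. Most of this stands and sets the severity. It does not remove the point, because adjustment keeps the same outcome and, apart from about one degree of freedom per covariate, does not lose precision.

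A reader might infer more than the documents support:

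- **That the comparison is biased or the outcome wrong.** It is neither, for the reasons just given.
- **That a large gain is established.** The documents do not give the pre-instillation share or its correlation with later time. The Introduction, discussing transplant recipients, suggests that longer procedures may reflect technical difficulty or attempts to control bleeding, and the latter falls after instillation. The SE formula also does not carry over directly to a Mann-Whitney test or a log-scale model.
- **That lavage and endobronchial biopsy come before instillation.** Criterion 4.11 permits them without fixing their order. Nebulised and gargled lidocaine are premedication and apparently off the clock.
- **That procedures after the biopsy are unrelated to treatment.** Bleeding could delay, shorten or cancel them.
- **That concurrent procedures are already captured for analysis.** Initial Evaluation has them reviewed in the chart to confirm eligibility. The item 9 data list does not include them.

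**Conclusion.** The point holds as a minor loss of precision. Outcome 7 includes time the drug cannot affect, and the planned tests make no allowance for it. Under independent segments and an assumed 25% or 50% share, adjustment would cut the standard error by 13% or 29%. Positive correlation makes the gain larger than the share implies; negative correlation makes it smaller or zero. The true figure is unknown until durations are observed. The unadjusted analysis remains valid, and overall duration remains a proper target.

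**What to change.** Keep overall duration as the outcome, and:

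1. Record the time of first instillation, or read it from the procedure video.
2. Add planned concurrent procedures as a data field, taken from the chart review. Use those planned, not those performed, because bleeding can change what is performed.
3. Prespecify a regression of overall duration on arm, insertion-to-first-instillation time and planned concurrent procedures. Check residuals, and use a robust method if they are skewed.
4. Report first instillation to final scope withdrawal as a supportive measure, read alongside early termination for bleeding (item 6). An interval ending at the last biopsy pass would be unsuitable: it omits haemostasis after the final biopsy and scores a procedure aborted for bleeding as faster.

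The cost is one time point per video, one data field and about one degree of freedom per covariate. The instillation time is needed anyway: the Safety Outcomes windows of 30 minutes and 3 hours run from instillation, and item 9 does not list it.
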